4. REGULATORY COMPLIANCE

Design of this study was developed in compliance with principles of the Good Clinical Practice (GCP) described in ISO 14155:2011 and requirements of ISO 14155-1-2008 “Clinical investigation management of medical devices.”

CHILDren with neuromuscular diseases – efficacy eVALuation of spinal deformity surgeRY via different pedicle screw fixation systems study
CHIVALRY study

Ethics review of study documents and further ethics support of the study will be conducted by the Local Ethics Committee (LEC) at at Federal state budgetary institution “Russian scientific center for traumatology and orthopedics” n.a. acad. G.A. Ilizarov” of the Ministry of Health of Russian Federation.

The study will be conducted in accordance herewith, current legislation of the Russian Federation and LEC requirements as governed by principles of the Declaration of Helsinki.

5. SEVERE ADVERSE EVENTS

Information on all severe adverse events (SAE) will be collected throughout the study.

Severe adverse event (SAE) – a medically unfavorable event (adverse event) resulting in one of the following:

- a) Fatal outcome;
- b) Major aggravation of patient's health due to:
 - 1) a life-threatening disease or injury, or
 - 2) a persistent function impairment or structural damage, or
 - 3) a condition requiring hospitalization or increased duration of inpatient stay;
 - 4) a condition requiring additional therapeutic intervention or surgery to prevent a life-threatening disease or injury.

Information on SAE will be collected throughout the study from the moment of signing the informed consent form. Reports on these effects will be sent to the LEC. These reports will contain the following information:

- Date of the SAE;
- Description of the SAE;
- Treatment of the SAE;
- Outcome;
- Evaluation of severity of the SAE and its connection with the index procedure.

The type and duration of SAE observation will depend on its classification; treatment will be conducted at the investigator's discretion. Patients will be followed up until SAE are resolved, patients withdraw from the study or the study is completed, whichever is the soonest. If a patient withdraws from the protocol before the study is completed, maximum efforts will be made to continue following a patient up until SAE are resolved or deemed persistent without the need in further action.

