3.8.5. Visit No. 4. Before discharge (ca. after 21 days)

The duration of inpatient stay is determined by standards of the healthcare institution and on the average amounts to 21 days (depending on the patient's clinical condition). The following study procedures will be performed before discharge:

- Physical examination;
- Spine X-ray: scoliotic and kyphotic deformity measurements (Cobb angle), static and dynamic imbalance in frontal and sagittal planes;
- Spine CT and verification of screw position;
- laboratory tests (clinical blood analysis, blood chemistry);
- documentation of serious adverse events.

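### SAE item b)4 omits surgery that averts lasting, non-life-threatening damage, so an unplanned revision within the index stay that does not prolong it can go unrecorded

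*Combined protocol and SAP*

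**What the plan says.** Section 5 defines an SAE as an adverse event that ends in death or in "Major aggravation of patient's health due to" one of four things:

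- b)1: a life-threatening disease or injury;
- b)2: "a persistent function impairment or structural damage";
- b)3: "a condition requiring hospitalization or increased duration of inpatient stay";
- b)4: "a condition requiring additional therapeutic intervention or surgery to prevent a life-threatening disease or injury".

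Item b)4 is the only one that names surgery.

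On scope, Section 5 states: "Information on all severe adverse events (SAE) will be collected throughout the study". Table 1 and the visit descriptions in Sections 3.8.3 to 3.8.7 likewise list only serious or severe adverse events. No collection of non-serious events, device events or reoperations is described. Section 3.2 includes all-cause hospitalization as a secondary endpoint but not reoperation or implant revision.

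On the index stay, Section 3.8.5 says: "The duration of inpatient stay is determined by standards of the healthcare institution and on the average amounts to 21 days". The same sentence adds that the stay depends on the patient's clinical condition. The pre-discharge visit includes "Spine CT and verification of screw position".

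**The concern.** Items b)2 and b)4 do not match. Lasting impairment or structural damage is serious if it happens, but an operation done so that it does not happen is not named. The definition can therefore lose a harm because re-operating averted it.

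Safety is half of the study purpose in Section 1.2, and the object of study is pedicle screw fixation. An unplanned return to theatre for a screw or rod is direct safety information about these constructs. If it is not an SAE, it goes neither into the SAE data nor into the reports that Section 5 sends to the ethics committee, and nothing else in the schedule would bring it into the safety summary of Section 6.

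**Working it through.** The plan states no figure on this point, so the check is a reading of each criterion against each kind of unplanned revision, followed by a search for another place where the event would be recorded.

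**Step 1. Which revisions meet a criterion?**

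| Unplanned revision | Captured by |
|---|---|
| (a) Needs readmission | b)3, and the hospitalization endpoint |
| (b) In the index stay, and lengthens it | b)3 |
| (c) In the index stay, after lasting impairment or structural damage has occurred | b)2 |
| (d) In the index stay, to prevent a life-threatening condition | b)4 |
| (e) In the index stay, averts lasting but non-life-threatening damage, stay not lengthened | none |

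Case (e) fails b)1 because life was not threatened. It fails b)2 because the damage was averted, b)3 because the patient was already in hospital and stayed no longer, and b)4 because the harm prevented was not life-threatening. The lead-in to b), which asks for a major aggravation of health, does not help: an averted harm is harder to describe in that way.

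**Step 2. Can case (e) happen?** The stay averages about 21 days, and Section 3.8.5 gives no planned discharge day for the individual patient. A revision in the first days could be absorbed by the remaining stay. Without a fixed discharge day, whether the stay was increased has no clear baseline, so capture under b)3 rests on individual judgement.

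**Step 3. Is it recorded elsewhere?**

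- Section 3.2: all-cause hospitalization catches readmissions, not an event inside the index stay.
- Section 3.8.8: unscheduled visits are follow-up visits.
- Section 3.8.5: the CT verifies screw position, but no item for a resulting reoperation is described.
- Table 1: the only event row is for serious adverse events.

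None of these records case (e) as an event.

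**Step 4. Size.** The documents give no reoperation rate, and none for case (e). With 70 planned patients (Section 1.3), each affected patient who is missed lowers the reported proportion by 1/70 = 1.4 percentage points. Within the groups of Section 3.3 the figure is 1/30 = 3.3 points (growing skeleton) or 1/40 = 2.5 points (mature skeleton). How many would be missed cannot be derived.

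**The case against.** The strongest reply is that most revisions are already caught: four of the five cases above meet a criterion. That stands, and it limits the point to case (e). A reader might infer that the definition counts an extra operation only when life is threatened. The documents do not support this, because b)2 and b)3 carry no life-threat test.

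A second reply is that the wording can be read more generously. In b)2, the qualifier for lasting effect need not govern structural damage, so a screw breach that was corrected might qualify. In b)3, a condition requiring hospitalization might include one needing repeat surgery in a patient already admitted. In b)4, injury might stand apart from life-threatening. The last reading is weak, since b)1 uses the same phrase as one unit. The first two are possible but not the natural readings. They make capture depend on who reads the form, which is itself a reason to settle the text.

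A third reply concerns the pre-discharge CT. A reader might infer that this scan systematically produces uncollected revisions, because it checks screw position near the end of the stay. The timing points the other way: a revision prompted at about day 21 would probably lengthen a stay that depends on clinical condition, and so meet b)3. The gap concerns earlier revisions.

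A reader might also infer a biased comparison between constructs. Section 3.3 describes the study as non-comparative, with the main groups set by skeletal maturity, and Section 3.2 lists no SAE or reoperation rate as an endpoint. The loss is to the safety description, not to a planned test.

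**Conclusion.** The point holds in a narrow form. An unplanned reoperation within the index stay that averts lasting, non-life-threatening damage without lengthening the stay meets none of b)1 to b)4 and has no other place to be recorded. This rests on the natural reading of b)2 to b)4 and on the documents' silence about any reoperation or non-serious event record.

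The number of such events is unknown. One could assume that 2% to 10% of patients fall in the gap and obtain 70 × 0.02 = 1.4 to 70 × 0.10 = 7 lost events, but that only restates an assumption with no source in the documents. Similarly, a report of 0 of 70 has an exact two-sided 95% upper limit of 1 − 0.025^(1/70) = 5.1%. The arithmetic is correct, but it does not show that the true rate is higher. The case for the change rests on the logical gap and the low cost of closing it.

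**What to change.** In Section 5, extend b)4 so that the harm to be prevented is the one now named there or "a persistent function impairment or structural damage", which is the b)2 wording.

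Add one sentence: every unplanned return to theatre and every unplanned implant revision is recorded on the SAE form, whatever its effect on length of stay. This removes the dependence on an undefined planned discharge day and on the lead-in about major aggravation.

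Limit that sentence expressly to unplanned procedures. Section 2 builds the group 1 rods with 2 cm left for distraction, so a rule covering any implant procedure could turn planned work on growing-rod constructs into SAEs.

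The change affects reporting only: a short edit to Section 5 and to the SAE form, with no new visit or procedure. The downside is a few more SAE reports and a slightly higher reported SAE rate.

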6. STATISTICAL ANALYSIS AND METHODS

Primary and additional quantitative efficacy and safety criteria will be summarized in shift tables and presented by means of descriptive statistics; the appropriate methods will be selected depending on the data. Missing data will be indicated as N/A and not considered in aggregate statistics. The significance of differences between data groups will be evaluated using the criteria depending on the number of observations and distribution type of parameter values within groups. Software: Statistical Package for the Social Sciences (SPSS), v. 22.0 (SPSS Inc., Chicago, IL, USA). T-criteria: 1) comparison of correction of sagittal and frontal spinal deformity components with graded FC parameters. Differences will be considered significant if two-sided $p < 0.05$.

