3.2. Endpoints

The primary endpoint is decrease in spine deformity grade by 1 or more (according to Chaklin classification) with stabilization or improvement in lung parameters in 12 months after the surgery.

Secondary endpoints are as follows:

1. Hospitalization by all causes
2. Improvement in life quality after surgery according to scales (VAS, GMFCS, RLAS, FIM, MACS) in 6 months and 12 months after surgery.

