3.3. Study design

This study is prospective, non-randomized, single-center, open and non-comparative; it involves two parallel groups of patients (children aged 10-18 years) with severe thoracic and lumbar spinal deformities at NMD.

Patients are divided into groups depending on skeletal maturity determined on the basis of an X-ray study of spinal and pelvic bones. The type of surgical correction will depend on the group.

1. Group of patients with spinal deformities corrected and stabilized with bilateral connector systems (growing skeleton).

Bone maturity grades I-III (Sadofyeva classification) or I-II (Risser classification).

Bilateral connector systems (“growing rods”) will be used in this group (N = 30).

2. Group of patients with spinal deformities corrected and stabilized with bilateral multiple fixation points (mature skeleton).

Bone maturity grades IV-V (Sadofyeva classification) or III-IV (Risser classification).

Inside this group (N=40) two subgroups are planned depending on varying anatomic characteristics thus allowing for specific treatment option:

- *Subgroup 1 – segmental fixation*
- *Subgroup 2 – intermittent (next nearest) segment fixation*

Patients will be enrolled in study groups in consecutive stages, according to enrollment criteria described above

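### The primary endpoint is a joint per-patient success, but section 6 plans no success proportion, denominator or confidence interval for it

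*Combined protocol and SAP*

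**What the plan says.** Section 3.2 (Endpoints) defines the primary endpoint as "decrease in spine deformity grade by 1 or more (according to Chaklin classification) with stabilization or improvement in lung parameters in 12 months" after surgery. The two parts are joined, so each patient either meets both or does not succeed.

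Section 6 is the whole statistical plan. For the primary and other criteria it states "Primary and additional quantitative efficacy and safety criteria will be summarized in shift tables and presented by means of descriptive statistics", and then "the appropriate methods will be selected depending on the data". For inference it offers a general sentence, "The significance of differences between data groups will be evaluated using the criteria depending on the number of observations and distribution type", and one specific item under T-criteria: "comparison of correction of sagittal and frontal spinal deformity components with graded FC parameters". Significance is judged at two-sided p < 0.05. Missing values are marked as not available and left out of the summaries.

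Section 3.3 describes a non-randomized, non-comparative study with two groups that receive different operations. In group 1, "Bilateral connector systems (“growing rods”) will be used in this group (N = 30"). Group 2 (N = 40) receives multiple-point fixation. No section gives an expected success rate, a benchmark, or a basis for the 30, the 40 or the total of 70.

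Table 1 (section 3.7) and section 3.8.7 make spirometry at the 12-month visit optional, to be done only when medically indicated.

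**The concern.** In a study without a comparator, the success proportion and its uncertainty are the main result. Section 6 gives p-values for differences between groups and for angle correction, but no planned estimate with uncertainty for the primary endpoint. It does not say whether that endpoint is reported per operation or pooled, or which patients form the denominator.

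Two things are at stake. First, a rate from 30 or 40 patients, printed without an interval, will be read as more exact than it is. Second, if the two components are summarised separately, for example a shift table of grades beside a summary of lung values, the reader cannot work out how many patients met both.

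**Working it through.** **Inputs from the documents.** Group 1 n = 30 and group 2 n = 40 (section 3.3); total 70 (section 1.3), and 30 + 40 = 70 agrees. The plan has no sample-size derivation to reproduce.

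**Assumed inputs.** The documents give no success rate, so all rates below are assumptions, shown over a range.

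**Step 1: what separate component summaries can show.** If a fraction a of patients meets the grade component and b meets the lung component, the joint fraction lies between max(0, a + b − 1) and min(a, b).

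- a = b = 0.8: from 0.8 + 0.8 − 1 = 0.60 up to 0.80, i.e. 42 to 56 of 70 patients.
- a = b = 0.7: from 0.40 up to 0.70, i.e. 28 to 49 of 70.
- a = 0.9, b = 0.7: from 0.60 up to 0.70, i.e. 42 to 49 of 70.

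The margins alone do not settle the joint rate. A per-patient cross-classification does. This step matters only if the components are in fact reported separately, which section 6 neither says nor rules out.

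**Step 2: the interval that is not planned.** For x successes in n patients, the exact (Clopper-Pearson) 95% limits are:

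- lower = Beta quantile at 0.025 with parameters (x, n − x + 1)
- upper = Beta quantile at 0.975 with parameters (x + 1, n − x)

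| Assumed rate | Group 1, n = 30 | Group 2, n = 40 | Pooled, n = 70 |
|---|---|---|---|
| 50% | 15/30: 31.3–68.7% | 20/40: 33.8–66.2% | 35/70: 37.8–62.2% |
| 70% | 21/30: 50.6–85.3% | 28/40: 53.5–83.4% | 49/70: 57.9–80.4% |
| 80% | 24/30: 61.4–92.3% | 32/40: 64.4–90.9% | 56/70: 68.7–88.6% |
| 90% | 27/30: 73.5–97.9% | 36/40: 76.3–97.2% | 63/70: 80.5–95.9% |

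Above 50% the intervals are asymmetric, so a single plus-or-minus figure understates the lower side. For 24/30 the distances are 80.0 − 61.4 = 18.6 points down and 92.3 − 80.0 = 12.3 points up.

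**Step 3: incomplete spirometry.** The table assumes that every patient has both components at 12 months. Suppose instead, as an illustration, that only 15 of the 30 patients in group 1 have 12-month spirometry and 12 of those 15 succeed.

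- Observed cases only: 12/15 = 80%, exact interval 51.9–95.7%.
- All 15 unmeasured patients counted as failures: 12/30 = 40%.
- All 15 counted as successes: (12 + 15)/30 = 27/30 = 90%.

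In this example the missing lung data alone move the estimate across 50 points, before sampling error. Not every unmeasured patient need be unknown: one whose grade did not fall has already failed the joint endpoint, which would lower the upper bound.

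**The case against.** The strongest reply is that section 6 leaves the matter open rather than getting it wrong. Descriptive statistics include counts and percentages. In the translated sentence the word quantitative may qualify only the additional criteria, and nothing says that grade and lung values will be tabulated apart. All of this stands. A reader might infer that the planned outputs cannot yield the joint success rate; the documents do not support that, because a count of patients meeting the endpoint, with its denominator, is the joint rate.

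A reader might also infer that nothing beyond shift tables and descriptives is planned. That is wrong too: between-group tests and a T-criterion are planned. They are simply not tied to the primary endpoint.

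Reporting by group is arguably implied, since the groups are defined by operation and section 6 refers to data groups. It is not stated for the primary endpoint.

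It can also be said that an interval can be computed later from any reported count and denominator. That is true if both are reported, but section 6 commits to neither, and the rule of dropping missing values leaves the denominator undefined. The choice of an exact interval over a Wilson interval is a preference; having an interval is not.

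**Conclusion.** The point holds as a gap in specification. Section 6 does not plan the success proportion, its denominator or a confidence interval for the joint endpoint, while it does plan significance tests in a study described as non-comparative.

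The omitted uncertainty is substantial. In group 1 the half-width of the exact interval is about 12 to 19 points, and in group 2 about 10 to 16 points, for assumed rates from 90% down to 50%. These are best cases that require complete 12-month lung data.

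A reader might infer that naming a proportion in section 6 would be enough to give a result for every patient. It would not: the endpoint needs 12-month lung data that the schedule makes optional, so success cannot be derived for everyone under the current text.

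This is an improvement the sponsor should make, not a fatal flaw. A count could still be produced under the present wording.

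**What to change.** In section 6, add for the primary endpoint:

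1. One success or failure per patient, requiring both components at Visit 6.
2. The success proportion separately for group 1 and group 2, each with a two-sided exact 95% interval. A pooled figure is supportive only.
3. A cross-table of grade fall (yes, no) by lung status (stable or improved, not, not measured).
4. The denominator, the number without 12-month spirometry in each group, and bounds that count those patients first as all failures and then as all successes.
5. Beside N = 30 and N = 40, the expected precision over a range of assumed rates, as limits rather than plus-or-minus figures: for example 50.6–85.3% for 21/30 and 53.5–83.4% for 28/40, with a note that these assume complete spirometry.

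Section 3.2 must be reconciled with Table 1 and section 3.8.7, because the endpoint depends on a measurement the schedule treats as optional. Section 3.2 should also say which lung parameters count and what qualifies as stabilization, since the success variable cannot be coded without this.

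The cost is a few lines of text and a little analysis work. The downside is that the published uncertainty will be visibly wide. The reporting changes alone do not alter conduct; whether the reconciliation does depends on how the sponsor resolves it.

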3.8.7. Visit No. 6. 12 months after the procedure

The following study procedures will be performed during a scheduled visit 12 months after the procedure:

- physical examination and clinical evaluation: physical status (body mass index);
- functional status and life quality (with VAS, FIM, MACS, GMFCS);
- spine X-ray: scoliotic and kyphotic deformity measurements (Cobb angle), static and dynamic imbalance in frontal and sagittal planes;
- laboratory tests (clinical blood analysis) (as an option if there is a medical condition);
- spirometry, ECG, echocardiography (as an option if there is a medical condition);
- Spine CT with evaluation of screw position and fusion mass (as an option, if there are signs of a bone block in the area of instrumental fixation according to radiographs of the spine);
- documentation of serious adverse events.

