3.8.9. Study withdrawal

Patients may withdraw from the study in the following situations:

- The follow-up period has completed;
- A patient is not available to follow-up;
- Patient death;
- A patient decided to withdraw from the study (refused to continue participation, moved to a different region);
- The investigator deemed patient withdrawal from the study necessary (for example, due to medical reasons or impossibility of adequate patient compliance with protocol requirements).

If a patient is considered not available to follow-up or refuses to continue participation or the investigator deems patient withdrawal from the study necessary, the investigator shall document patient withdrawal and the reason for withdrawal. After a patient has withdrawn from the study, further data collection and additional visits are not performed.

After their withdrawal from investigation, a patient will still obtain the normal treatment comparable with that as rendered during the regular surgical correction.

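### Read together, sections 6 and 3.8.9 drop patients who die before 12 months from the primary-endpoint denominator, and no analysis set or counting rule says otherwise

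*Combined protocol and SAP*

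**What the plan says.** Section 3.2 sets a binary primary endpoint at 12 months after surgery: "decrease in spine deformity grade by 1 or more (according to Chaklin classification) with stabilization or improvement in lung parameters". A patient needs a result at that time to be classed as a success.

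Section 3.8.9 lists the ways a patient leaves the study. They include "Patient death", loss to follow-up, refusal, and "The investigator deemed patient withdrawal from the study necessary (for example, due to medical reasons" or poor compliance). It then states: "After a patient has withdrawn from the study, further data collection and additional visits are not performed". For loss, refusal and investigator withdrawal, "the investigator shall document patient withdrawal and the reason for withdrawal". Deaths are captured separately, because section 5 defines a fatal outcome as a severe adverse event.

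Section 6 has one sentence on absent results: "Missing data will be indicated as N/A and not considered in aggregate statistics". It names no analysis set (enrolled, operated or completers), no rule for counting deaths or withdrawals, and no sensitivity analysis.

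Planned sizes are 70 in all (section 1.3), as 30 and 40 (section 3.3). Section 3.6 excludes patients with life expectancy under 12 months.

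**The concern.** The 12-month success rate is the study's main efficacy result. A reader will probably take it as the chance that an operated child benefits. Under the written rule it describes only children who have a 12-month result. A child who died before then is a known non-success for that question, yet the rule treats the child like someone whose film was mislaid. Because the study is open and single-center, leaving the denominator unstated also means it can be settled after results are known.

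**Working it through.** **Plan's own figures.** Only the group sizes can be checked: 30 + 40 = 70, which agrees. The documents give no power, target success rate, expected mortality or dropout. Every input below other than 70, 40 and 30 is an assumption.

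**Deaths.** Let n be the number operated, k the deaths before 12 months and s the successes, with no other missing results. The written rule reports p = s/(n − k). The all-operated rate is s/n. The difference is

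s/(n − k) − s/n = p·k/n,

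which is above zero whenever s and k are above zero.

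Per death, at an assumed p = 75%:
- n = 70: 0.75/70 = 1.1 points
- n = 40: 0.75/40 = 1.9 points
- n = 30: 0.75/30 = 2.5 points

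At n = 70, p = 60% gives 0.60/70 = 0.9 points and p = 90% gives 0.90/70 = 1.3 points.

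Examples with two deaths:
- All patients: 51/68 = 75.0% reported against 51/70 = 72.9%, a difference of 2.1 points.
- Group of 30: 21/28 = 75.0% reported against 21/30 = 70.0%, a difference of 5.0 points.

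For scale, the 95% Wilson interval for 51/68 runs from 63.6% to 83.8%, about 20 points wide.

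**Medical withdrawals.** Suppose 4 of 70 are withdrawn and 49/66 = 74.2% is reported. If j of the four would have succeeded, the full rate is (49 + j)/70:

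| j | Full rate | Reported minus full |
|---|---|---|
| 0 | 70.0% | +4.2 points |
| 2 | 72.9% | +1.4 points |
| 3 | 74.3% | about 0 |
| 4 | 75.7% | −1.5 points |

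The sign depends on outcomes that nobody observes.

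**Mixed losses.** Suppose 45/60 = 75.0% is reported, with 2 deaths, 2 medical withdrawals and 6 other losses. Counting only the deaths as non-response gives 45/62 = 72.6%. With all 8 remaining patients as failures the rate is 45/70 = 64.3%; with all 8 as successes it is 53/70 = 75.7%. The reported 75.0% lies inside these bounds, so the direction of the total error is not fixed.

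**The case against.** The strongest reply is that the plan nowhere calls a death missing data. Section 3.8.9 lists death beside completion of follow-up, so the list can be read as describing how participation ends, not as an analysis rule. A death is a recorded event under section 5, and an analyst could classify it as a known non-response without breaching section 6. This stands in part: dropping deaths is an inference from sections 6 and 3.8.9 taken together. But section 6 is the only rule for an absent result, a patient who has died has no 12-month result, and nothing overrides that rule.

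A second reply is that a rate among patients with a result is a legitimate quantity, and the plan never promises an all-operated rate. That is fair, but the plan does not state which quantity it reports. A descriptive rate still needs a denominator.

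A third reply concerns size, and it stands. A few deaths move the rate by much less than its sampling error. No success threshold is set, the design is labelled non-comparative, and the life-expectancy exclusion should keep deaths few.

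A reader might also infer that every kind of missing result inflates the rate. The documents do not support this: only deaths have a known direction. Nor should the conditional 12-month spirometry ("spirometry, ECG, echocardiography (as an option if there is a medical condition") be used to enlarge this point. It could leave more results missing than deaths do, but it is a separate conflict with the lung component of the endpoint, and its direction is unknown.

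**Conclusion.** The point holds as a should-fix item of limited consequence. Followed as written, the plan removes deaths from the denominator of an endpoint they cannot meet. The reported rate then exceeds the all-operated rate by p·k/n: about 1.1 points per death at n = 70 and 2.5 at n = 30, if the reported rate is 75%. This rests on reading the two sections together, on at least one death and one success occurring, and on taking all operated patients as the reference. For medical withdrawals, refusals, losses and returners without spirometry, the finding is only that no rule exists. The numbers can largely be recovered from the documented withdrawal reasons and the severe adverse event records. What is lacking is a rule fixed in advance and a commitment to report those numbers.

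**What to change.** In section 6, for the primary endpoint, replace the missing-data sentence with the following:

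- The analysis set is all operated patients.
- Death before 12 months counts as non-response.
- All other missing results, including medical withdrawals, are shown as a complete-case rate with a best-case bound (all successes) and a worst-case bound (all failures).
- Numbers missing are reported by reason, using the reasons documented under 3.8.9 and the severe adverse event records.

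The 12-month film is unconditional ("spine X-ray: scoliotic and kyphotic deformity measurements (Cobb angle"), so it is tempting to count untested returners whose grade did not fall as failures. They should not enter the complete-case rate. Success would still require spirometry, so the shift runs one way only: in an assumed example, 14/18 = 77.8% becomes 14/(18 + 12) = 46.7%. Such films may be used only to tighten the best-case bound, and only if the Chaklin grade is read from that film. The documents mention Cobb measurement and give no mapping to the grade.

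Separately, reconcile the spirometry passages with the lung component in section 3.2. Table 1 in section 3.7 marks the whole row and the 12-month cell as done only for medical reasons. Section 3.8.2 lists the screening test without condition, and section 3.8.7 makes the 12-month test optional.

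The cost is a few sentences and a little extra analysis. The rate will look slightly less favourable if deaths occur, and the bounds will be wide if many results are missing.
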